12.2 Subject demographics and other baseline characteristics

Unless otherwise specified, for subject demographics and other baseline characteristics, analyses will be based on the randomized set.

Demographics and baseline characteristics

Summary statistics will be presented for continuous demographic and baseline characteristic variables for each treatment group and for all subjects in the randomized set. The number and percentage of subjects in each category will be presented for categorical variables for each treatment group and all subjects.

Medical history

Any condition entered as medical history or current medical conditions at baseline will be coded using the MedDRA dictionary. They will be summarized by system organ class and preferred term of the MedDRA dictionary. Summaries for cardiovascular and psoriasis specific medical history will be provided as well.

12.3 Treatments

12.3.1 Study treatment

The analysis of study treatment data will be based on the safety set.

The duration of exposure to study treatment will be summarized by treatment group. In addition, the number of subjects with exposure of at least certain thresholds (eg, any exposure, ≥ 1 week, ≥ 2 weeks, ≥ 3 weeks, ≥ 4 weeks, ≥ 8 weeks, etc.) will be displayed.

Duration of exposure of a treatment will be defined as the time from first dose of the treatment to the time of treatment switch (for subjects who switch from placebo to active treatment) or minimum of last dose of the treatment + 84 days and last visit date.

12.3.2 Prior and concomitant medication

Prior and concomitant medications will be summarized by treatment group for the different periods in separate tables.

Prior medications are defined as treatments taken and stopped prior to first dose of study treatment. Any medication given at least once between the day of first dose of randomized study treatment and the last day of study visit will be a concomitant medication, including those which were started pre-baseline and continued into the treatment period.

Medications will be presented in alphabetical order, by Anatomical Therapeutic Classification (ATC) codes and grouped by anatomical main group. Tables will also show the overall number and percentage of subjects receiving at least one treatment of a particular ATC code and at least one treatment in a particular anatomical main group.

Psoriasis specific pre-study treatments, number of pre-study systemic and biologic psoriasis therapies as well as reason for discontinuation will be presented.

In addition, medical procedures and significant non-drug therapies as coded in MedDRA will be summarized.

12.4 Analysis of the primary variables

Details of the testing strategy including primary endpoints are provided in [Section 12.4.2](#).

12.4.1 Definition of primary endpoint(s)

The co-primary efficacy variables are PASI 75 response at Week 12 and IGA mod 2011 0 or 1 response at Week 12. The analysis of the co-primary variables will be based on the FAS.

12.4.2 Statistical model, hypothesis, and method of analysis

The co-primary endpoints of this study are PASI 75 response and IGA mod 2011 0 or 1 response at Week 12.

The statistical hypothesis is that secukinumab 300 mg (2 mL AI) is not superior to placebo with respect to the proportion of subjects with PASI 75 response and IGA mod 2011 0 or 1 response at Week 12.

Let p_j denote the proportion of PASI 75 responders at Week 12 for treatment group j and r_j denote the proportion of IGA mod 2011 0 or 1 responders at Week 12 for treatment group j , $j = 1, 0$ where,

- 0 corresponds to placebo
- 1 corresponds to secukinumab 300 mg (2 mL AI)

The following hypothesis will be tested:

- $H_1: p_1 - p_0 \leq 0$ versus $H_{A1}: p_1 - p_0 > 0$,
- $H_2: r_1 - r_0 \leq 0$ versus $H_{A2}: r_1 - r_0 > 0$

In other words:

H_1 : Secukinumab 300 mg (2 mL AI) is not superior to placebo with respect to PASI 75 response at Week 12

H_2 : Secukinumab 300 mg (2 mL AI) is not superior to placebo with respect to IGA mod 2011 0 or 1 response at Week 12

The primary analysis method will be the logistic regression with treatment group (secukinumab 2mL AI vs Placebo); baseline bodyweight strata and baseline PASI score as explanatory variables. Odds ratios will be computed for comparisons of secukinumab dose regimen versus placebo utilizing the logistic regression model fitted. In case of response rates of 0% or of 100% in one of the treatment groups, Fisher's exact test will be applied. Confidence intervals for risk difference will be derived based on the exact method.

If logistic regression model does not converge the following steps will be performed:

1. Run the PROC GENMOD procedure with EXACT statement;
2. If convergence not reached, remove the covariates from the model one by one until convergence is reached; start with continuous covariates (baselines PASI score), followed by removing categorical covariates (i.e., weight stratum etc.,);
3. If convergence not reached, perform Fisher's exact test.

In case of response rates of 0% or of 100% in one of the treatment groups, Fisher's exact test will be applied. Confidence intervals for risk difference will be derived based on the exact method.

The hypotheses H_1 and H_2 will both be tested at level 2.5% (one-sided), and significant results will only be achieved if both tests are rejected. If only one hypothesis is rejected and the other hypothesis is not rejected, superiority of secukinumab 300 mg (2 mL AI) has not been demonstrated.

12.4.3 Handling of missing values/censoring/discontinuations

The following imputation methods will apply to the missing data:

- Response variables based on PASI score and IGA mod 2011 categories will be imputed with multiple imputations (MI) method as primary imputation method. MI is a simulation based approach where missing values are replaced by multiple Bayesian draws from the conditional distribution of missing data given the observed data and covariates, creating multiple completed data sets. These completed data sets can then be analyzed using standard methods. Within this analysis the PASI score or IGA mod 2011 categories will be imputed and response variables will be derived based on the imputed scores. In the multiple imputation analysis the response status will be imputed based on the individual treatment arm information.
- Non-responder imputation will be used as sensitivity method: Missing values with respect to response variables based on PASI score and IGA mod 2011 categories will be imputed with non-response regardless to the reason for missing data (eg, premature study discontinuation, missed visit, administrative issues), exceptions will apply to the following:
 - If a subject dropped out of the study prior to last scheduled efficacy assessment and being responder consecutively at least for two preceding visits, the subject will be imputed as responder for the last scheduled visit.
 - If a subject who was responder at visit $x-1$ and visit $x+1$ but has missing data at visit x , then the subject will be imputed as responder for visit x as long as the distance between the scheduled visits $x-1$ and x is 4 weeks or less, or the distance between the scheduled visits x and $x+1$ is 4 weeks or less. Otherwise missing data will be imputed with non-response.

12.4.4 Sensitivity analyses

Co-primary variables will be evaluated using the logistic regression as described in primary analysis method with non-responder imputations as sensitivity analyses.

12.5 Analysis of secondary endpoints

The key secondary endpoint of this study is PASI 90 response at Week 12.

Testing strategy

As stated in [Section 12.4.2](#), the hypotheses H_1 and H_2 will be included in co-primary testing procedure. Each hypotheses is tested at $\alpha = 2.5\%$ (one-sided). The testing sequence will continue to key secondary endpoint PASI 90 at $\alpha = 2.5\%$ (one-sided) only if both H_1 and H_2 have been rejected at α (one-sided) such that a family-wise type-I-error of α (one-sided) is kept.
 H_3 : secukinumab 300 mg (2 mL AI) is not superior to placebo with respect to PASI 90 response at Week 12

PASI 90 response will be analyzed analogously to the primary endpoints at Week 12, i.e., the logistic regression model with treatment group, baseline bodyweight strata and baseline PASI score as exploratory variables. Odds ratios will be computed for comparisons of secukinumab versus placebo utilizing the logistic regression model fitted.

12.6 Analysis of other secondary and exploratory endpoints

12.6.1 Efficacy Endpoints

PASI 50, PASI 75, PASI 90, PASI 100 and IGA mod 2011 0 or 1 response over time

Summary statistics for PASI 50, PASI 75, PASI 90, PASI 100 and IGA mod 2011 0 or 1 response by visit will be presented in contingency tables and will include absolute and relative frequencies. Confidence intervals for response rates will be derived as well based on the exact method.

For PASI 50, PASI 75, PASI 90, PASI 100 and IGA mod 2011 0 or 1 response at each visit, comparisons between 2mL AI vs placebo and 2mL AI vs 1mL PFS x 2 will be conducted using logistic regression model with treatment group, body weight stratum, and baseline PASI as effects.

Figures will be provided as well displaying estimates for responder rates by treatment including confidence intervals.

PASI score over time

Summary statistics will be provided for absolute PASI scores as well as for percent change from baseline by visit and treatment group. Figures will also be provided.

IGA mod 2011 score over time

Summary statistics for the IGA mod 2011 score over time will be presented by visit and by treatment group in contingency tables. Figures will also be provided.

12.6.2 Safety Endpoints

All safety evaluations will be performed on the safety set.

Analysis of adverse events will be based on treatment emergent events, which are defined as events started after the first dose of study treatment and within 84 days after the last study treatment, or events present prior to the first dose of study treatment but increased in severity based on preferred term within 84 days after the last study treatment.

Other safety variables will be based on on-treatment events, which are defined as any events that happened after first dose of study treatment and on or before last dose + 84 days.

Adverse events

Treatment emergent AEs will be summarized for each treatment group by presenting the number and percentage of subjects with all/any AEs, AEs in each primary system organ class and each individual AE (preferred term). Summaries will also be presented for AEs by severity and for study treatment related AEs. If a subject reported more than one adverse event with the same preferred term, the adverse event with the highest severity will be presented. If a subject reported more than one adverse event within the same primary system organ class, the subject

will be counted only once with the highest severity at the system organ class level, where applicable.

Tabulated summaries will be presented for Treatment Period 1 and for the entire study (Treatment Period 1 combined with Treatment Period 2)

Confidence intervals for relative frequencies will be derived as well according to the score method including continuity correction by [Newcombe 1998](#).

Separate summaries will be provided for death, serious adverse event, other significant adverse events leading to discontinuation and adverse events leading to study treatment discontinuation.

A graphical display of relative frequencies within system organ classes will be presented.

Exposure adjusted analyses in terms of incidence rate will be provided combining all the study periods.

Laboratory data

The summary of laboratory evaluations will be presented for three groups of laboratory tests (hematology and serum chemistry). Descriptive summary statistics for the change from baseline to each study visit will be presented. These descriptive summaries will be presented by test group, laboratory test and treatment group. Change from baseline will only be summarized for subjects with both baseline and post baseline.

For each parameter, the maximum change from baseline within each study period will be analyzed analogously.

Shift tables with respect to Common Toxicity Grade Criteria (CTC) and normal ranges will be provided. These summaries will be presented by laboratory test and treatment group. Shifts will be presented for most extreme values post-baseline.

Incidence rates of notable abnormalities will be presented ([Appendix 1](#)).

Vital signs

Analysis of the vital sign measurements using summary statistics for the change from baseline for each post-baseline visit will be performed. These descriptive summaries will be presented by vital signs and treatment group. Change from baseline will only be summarized for subjects with both baseline and post-baseline values.

All information collected will be listed by subject and abnormal values will be flagged ([Appendix 1](#)).

12.6.3 Health-related Quality of Life - Dermatology Life Quality Index (DLQI)

Summaries will be based on the FAS and will be presented separately for each treatment group.

For each of the seven scores the percentage change from baseline will be derived. Summary statistics will be provided for absolute values as well as for the percentage change by visit and treatment group.

The absolute value and the percentage change from baseline of DLQI total score will be analyzed with the Van-Elteren test using type-II weights, for between-treatment comparison of the two secukinumab treatment groups versus placebo. The Van-Elteren test will be performed at each visit. Language of the questionnaire will be the stratum adjusted for in the Van-Elteren test. In addition, stratified Hodges-Lehmann estimates for the median as well as confidence intervals will be derived for the absolute values and percentage change to baseline for each treatment group as well as for treatment comparison between two secukinumab treatment groups versus placebo.

It is understood that conclusions obtained from the confidence intervals of these estimates (mean or Hodges-Lehmann estimates for the median) will not be completely consistent with the testing results (Van-Elteren test) which constitute the key analysis for drawing conclusions.

In addition, summary statistics will be provided for number of subjects achieving DLQI 0 or 1. Treatment groups will be compared by means of Fisher's exact test.

[figure not shown]
12.6.4 Self-Injection Assessment Questionnaire (SIAQ)

Summary statistics for the domain scores as well as item scores will be provided by visit and treatment group.

Item and domain scores from the PRE module taken before the first self-injection at Randomization will be compared with the corresponding item and domain scores (Feeling about injections, Self-confidence domains and overall satisfaction of self-injection item) from the POST module taken after self-injections. Change from the PRE module to POST module in item and domain scores will be summarized by visit and treatment group.

12.6.5 Resource utilization

Not applicable.

12.6.7 DNA

Not applicable.

12.6.8 Biomarkers

Not applicable.

12.7 Interim analyses

A Week 16 analysis will be performed when all subjects have completed the Visit Week 16. Additional interim analyses may be performed to support health authority interactions as necessary. Trial modifications are not planned based on any interim analysis.

At the end of study, a final analysis of all data collected up to last study visit (Week 52) will be performed when all subjects have completed the last study visit.

12.8 Sample size calculation

A response rate of 8% for PASI 75 response and IGA mod 2011 0 or 1 response in the placebo group is expected, whereas a response rate of 62% for PASI 75 response and 55% for IGA mod 2011 0 or 1 is the anticipated response in the secukinumab 300 mg (2 mL auto-injector s.c.) group.

Placebo-response rates between 3% and 7% have been reported in ([Papp et al 2005](#), [Menter et al 2008](#), [Leonardi et al 2008](#)).

12.8.1 Primary endpoint(s)

With respect to the co-primary endpoints (PASI 75 response and IGA mod 2011 0 or 1 response at Week 12), the type-I-error will be 2.5% one-sided for comparison. With 40 subjects per group and assuming a response rate of 8% for PASI 75 response and IGA mod 2011 0 or 1 response in the placebo group, the power to show a response rate of 62% for PASI 75 response and 55% for IGA mod 2011 0 or 1 response in the secukinumab 300 mg (2 mL auto-injector s.c.) group based on Fisher's exact test (nQuery Advisor 7.01, two group Fisher's-exact test of equal proportions) is above 99% for PASI 75 response and IGA mod 2011 0 or 1 response.

12.8.2 Secondary endpoint(s)

The study should be sufficiently powered (above 90%) to show a response rate of 46% points in PASI 90 response if the placebo rate is assumed as 8%.

13 Ethical considerations and administrative procedures

13.1 Regulatory and ethical compliance

This clinical study was designed and shall be implemented, executed and reported in accordance with the ICH Harmonized Tripartite Guidelines for Good Clinical Practice, with applicable

local regulations (including European Directive 2001/20/EC, US CFR 21), and with the ethical principles laid down in the Declaration of Helsinki.

13.2 Responsibilities of the investigator and IRB/IEC

Before initiating a trial, the investigator/institution must obtain approval/favorable opinion from the Institutional Review Board/Independent Ethics Committee (IRB/

IEC) for the trial protocol, written informed consent form, consent form updates, subject recruitment procedures (eg, advertisements) and any other written information to be provided to subjects. Prior to study start, the investigator is required to sign a protocol signature page confirming his/her agreement to conduct the study in accordance with these documents and all of the instructions and procedures found in this protocol and to give access to all relevant data and records to Novartis monitors, auditors, Novartis Quality Assurance representatives, designated agents of Novartis, IRBs/IECs, and regulatory authorities as required. If an inspection of the clinical site is requested by a regulatory authority, the investigator must inform Novartis immediately that this request has been made.

13.3 Publication of study protocol and results

The protocol will be registered in a publicly accessible database such as clinicaltrials.gov and as required in EudraCT. In addition, after study completion and finalization of the study report the results of this trial will be submitted for publication and posted in a publicly accessible database of clinical trial results, such as the Novartis clinical trial results website and all required Health Authority websites (eg, Clinicaltrials.gov, EudraCT etc.)

For details on the Novartis publication policy including authorship criteria, please refer to the Novartis publication policy training materials that were provided to you at the trial investigator meetings.

13.4 Quality Control and Quality Assurance

Novartis maintains a robust Quality Management System that includes all activities involved in quality assurance and quality control, to ensure compliance with written Standard Operating Procedures as well as applicable global/local GCP regulations and ICH Guidelines.

Audits of investigator sites, vendors, and Novartis systems are performed by auditors, independent from those involved in conducting, monitoring or performing quality control of the clinical trial. The clinical audit process uses a knowledge/risk based approach.

Audits are conducted to assess GCP compliance with global and local regulatory requirements, protocols and internal Standard Operating Procedures, and are performed according to written Novartis processes.

14 Protocol adherence

This protocol defines the study objectives, the study procedures and the data to be collected on study participants. Additional assessments required to ensure safety of subjects should be administered as deemed necessary on a case by case basis. Under no circumstances including

incidental collection is an investigator allowed to collect additional data or conduct any additional procedures for any purpose involving any investigational drugs under the protocol, other than the purpose of the study. If despite this interdiction prohibition, data, information, observation would be incidentally collected, the investigator shall immediately disclose it to Novartis and not use it for any purpose other than the study, except for the appropriate monitoring on study participants.

Investigators ascertain they will apply due diligence to avoid protocol deviations. If an investigator feels a protocol deviation would improve the conduct of the study this must be considered a protocol amendment, and unless such an amendment is agreed upon by Novartis and approved by the IRB/IEC and health authorities, where required, it cannot be implemented.

16.1 Appendix 1: Clinically notable laboratory values and vital signs

The following criteria will be used to define expanded limits and notable abnormalities of key laboratory tests. Notable values for blood pressure and pulse are presented in [Table 8-4](#).

No specific action is pre-defined within this protocol to respond to specific abnormal laboratory values, as it will be decided by the investigator whether and which specific action needs to be taken to respond to any abnormal values, taking into account the overall status of the subject.

Liver Function and Related Variables

Alanine transaminase (ALT) (SGPT):	> 3 x Upper Limit of Normal (ULN)
Aspartate transaminase (AST) (SGOT):	> 3 x ULN
Total bilirubin:	> 2 x ULN
Alkaline phosphatase:	> 2.5 x ULN

Renal Function

Creatinine (serum):	> 1.5 x ULN
---------------------	-------------

[figure not shown]
Hematology Variables

Hemoglobin:	≥ 20 g/dL decrease from baseline
Platelet count:	< Lower Limit of Normal (LLN)
White blood cell count:	< 0.8 x LLN
Neutrophils:	< 0.9 x LLN
Eosinophils:	> 1.1 x ULN
Lymphocytes:	> 1.1 x ULN

Urinalysis Variable

Protein urine dipstick:	++*
-------------------------	-----

* ++ is ≥ 100 mg/dL

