 - Significant medical problems, including but not limited to the following: uncontrolled hypertension (repeated values of systolic BP \geq 160 mmHg and/or diastolic BP \geq 95 mmHg), congestive heart failure (New York Heart Association status of class III or IV).
 - Serum creatinine level exceeding 2.0 mg/dL (176.8 μ mol/L).
 - Total white blood cell (WBC) count $<$ 2,500/ μ L, or platelets $<$ 100,000/ μ L or neutrophils $<$ 1,500/ μ L or hemoglobin $<$ 8.5 g/dL at Screening.
10. Active systemic infections during the last two weeks (exception: common cold) prior to randomization or any infection that reoccurs on a regular basis.
11. History of an ongoing, chronic or recurrent infectious disease, or evidence of tuberculosis (TB) infection as defined by a positive central laboratory test result at screening. Subjects with a positive test result may participate in the study if further work up (according to local practice/guidelines) establishes conclusively that the subject has no evidence of active tuberculosis. If presence of latent tuberculosis is established, then treatment must have been initiated and maintained according to local country guidelines prior to randomization.
12. Past medical history record or current infection with Human Immunodeficiency Virus, hepatitis B or hepatitis C prior to Randomization.
13. History of lymphoproliferative disease or any known malignancy or history of malignancy of any organ system treated or untreated within the past 5 years, regardless of whether there is evidence of local recurrence or metastases (except for Bowen's disease, or basal cell carcinoma or actinic keratoses that have been treated with no evidence of recurrence in the past 12 weeks; carcinoma in situ of the cervix or non-invasive malignant colon polyps that have been removed).
14. Inability or unwillingness to undergo repeated venipuncture (eg, because of poor tolerability or lack of access to veins) or to self-administer sub-cutaneous injections.
15. History or evidence of ongoing alcohol or drug abuse, within the last six months before Randomization.
16. History of hypersensitivity to any of the study treatments or its excipients or to drugs of similar chemical classes.

6 Treatment

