8.4.1 Laboratory evaluations

A central laboratory will be used for analysis of all specimens listed below, unless noted otherwise. Details on the collections, shipment of samples and reporting of results by the central laboratory are provided to investigators in the laboratory manual. Refer to the Laboratory Manual for identification of laboratory reference range values and the schema for notification of site staff and Novartis for out of range values.

Subjects should avoid smoking within the hour preceding the blood draws.

[Appendix 1](#) shows the extended laboratory ranges that are considered clinically notable.

No specific action is pre-defined within this protocol to respond to specific abnormal laboratory values, as it will be decided by the investigator whether and which specific action needs to be taken to respond to any abnormal values, taking into account the overall status of the subject.

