2.1 Data analysis general information

Novartis will be performing both Week 16 primary analysis and final analysis. Statistical software SAS version 9.4 or later will be used.

Data up to Week 16 will be presented for the Week 16 primary analysis and all data will be presented for final analysis.

Summary statistics for continuous variables will include N, mean, standard deviation, minimum, lower quartile, median, upper quartile, maximum. Summary statistics for discrete variables will be presented in contingency tables and will include absolute and relative frequencies.

The p-values will be presented as one-sided for hypothesis testings and as two-sided for other analysis. Two-sided 95% confidence intervals will be displayed. If not otherwise specified, hypothesis testings will be based on one-sided p-values that the treatment effect is in favor of Secukinumab. The level of significance will be set to 2.5% (one-sided, family-wise type-I-error). The 95% confidence intervals will not be used for decision making; they will only be used for estimation and will therefore always be two-sided.

All listings will be presented by treatment sequence.

Footnotes on outputs will be kept to a minimum also for outputs not covered in [MAP TLF shells](#).

Footnotes will generally be provided for

- abbreviations used in the output; abbreviations used on several outputs, e.g. for listings in [Appendix 16.2](#) can be presented on a separate page and do not have to be repeated as footnotes on each listing
- sorting order of categories, e.g. for sorting within MedDRA (Medical Dictionary for Regulatory Activities) hierarchy levels
- MedDRA version used for reporting of MedDRA coded data

Footnotes will generally NOT be given for

- units displayed on the output
- interpretation of results (e.g. “odds ratio larger than 1 favors active treatment”)
- information that can be retrieved from the statistical section of the clinical study report (CSR) unless it is not identifiable from the output, e.g.
 - explanation of analysis model used unless results of more than one model are displayed on an output
 - derivations of variables (e.g. BMI will not be explained on a footnote)
- information that will be provided in the clinical study protocol and/or methods section of the CSR (e.g. baseline definition if this is specified in the statistical section of the CSR)

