Post-baseline safety	Summary visit information (e.g. laboratory values, vital signs, etc.)	The (non-missing) measurement closest to the target day will be used. In the event two measurements are taken equally apart (e.g., 1 day before target date and 1 day after), the earlier one will be used. If two measurements are taken on the same day then select the first one (using the time). If two measurements are taken on the same date/time then use the first eCRF visit number (assuming this is the planned visit). If two measurements are taken on the same date/time/eCRF visit number then take the average value of these two results.
Post-baseline safety	Notable abnormalities (e.g. vital signs) and CTCAE grades for laboratory values	The most extreme measurement in the window will be used. Note this means a subject can have a notably high and notably low measurement within an analysis period.

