2.8.1 Adverse events (AEs)

For adverse events and other binary safety variables crude incidence and exposure time-adjusted incidence will be derived as described below and summarized in [Table 2-8](#).

All adverse events are summarized based on treatment emergent only. The definition for “treatment emergent” is as below:

- events started after the first dose of study medication or events present prior to the first dose of study medication but increased in severity based on preferred term
- and started prior to the last dose plus 84 days (inclusive)

All adverse events will be listed with “treatment emergent” flag displayed.

Table 2-8 Overview of analyses on some safety endpoints

Analysis period	AEs & SPP/RMP risks	SAEs	AEs-SMQ	AEs by severity	study treatment related AEs, death & other significant AEs	notables (lab/vitals)
treatment period 1 (up to week 12)	•crude incidence	•crude incidence				
Entire treatment period (including all data)	•crude incidence •exp.time adjusted incidence*	•crude incidence	•crude incidence			

*Note, Exposure adjusted incidence rates will be provided and follow the guideline as below:

- Primary SOC level for AE and SAE
- Level 1 for risks and SMQ
- PT level for SAE
- PT level for AE $\geq 2\%$ or incidence rate per 100 subject years ≥ 5.0 in any treatment group
- Other selected AEs of special interest on lower levels (e.g. PT or SMQ level 2), if appropriate

The crude incidence of treatment emergent adverse events will be presented for the treatment period up to Week 16 LPLV for W16 primary analysis, and treatment period including all data for final analysis. The crude incidence of treatment emergent adverse events will be summarized by primary System Organ Class (SOC) and Preferred Term (PT). Confidence intervals for the crude rate will be derived using the score method including continuity correction (Newcombe 1998) as described in [Section 5.4.5](#). In addition, exposure time-adjusted incidence rates will be provided for the treatment period including all data (see [Section 5.4.6](#)).

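### Protocol Appendix 1 calls hemoglobin notable after a fall of at least 20 g/dL, which no subject with a baseline below 20 g/dL can reach

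*Protocol*

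**What the plan says.** The hematology block of Protocol 16.1 (Appendix 1) gives the hemoglobin criterion as "≥ 20 g/dL decrease from baseline". Three parts of the protocol use this appendix:

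- Section 8.4.1 says that it "shows the extended laboratory ranges that are considered clinically notable".
- Section 10.1.1 describes it as the source of alert ranges for laboratory abnormalities.
- Section 12.6.2 refers to it for a planned output: "Incidence rates of notable abnormalities will be presented".

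The appendix also states: "No specific action is pre-defined within this protocol to respond to specific abnormal laboratory values".

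Elsewhere hemoglobin appears on a much lower scale. Protocol 5.2 excludes subjects whose value is below "8.5 g/dL at Screening", and SAP Table 2-9 places the CTCAE grade boundaries at 100 and 80 g/L.

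The SAP is unclear about laboratory notables. Table 2-8 keeps a column headed "notables (lab/vitals". Table 2-4 has a row for "Notable abnormalities (e.g. vital signs) and CTCAE grades for laboratory values". Section 2.8.3 analyses hemoglobin by CTCAE grade without citing Appendix 1. Section 4, which lists the analyses dropped from the protocol, does not mention laboratory notables.

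**The concern.** A criterion that cannot be met still fills a row in a safety table, and the row shows zero. A reader comparing arms could take that zero as evidence that no large hemoglobin falls occurred, when the definition alone fixed it.

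The same line is one of the ranges that investigators are pointed to when they review laboratory values, so it is also empty as a prompt at the sites.

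The SAP offers no hemoglobin-decrease definition of its own. A programmer would have to apply a threshold that cannot be met or leave out a protocol-planned analysis without any record of it.

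**Working it through.** The plan derives no figure here, so there is nothing to reproduce. The check is a bound, followed by a trace of which outputs depend on it.

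**Inputs**
- Required fall: 20 g/dL (Protocol 16.1). In the SAP's unit, 20 × 10 = 200 g/L.
- Screening limit: 8.5 g/dL (Protocol 5.2). No upper limit is given.
- CTCAE boundaries: 100 g/L = 10 g/dL (grade 1/2) and 80 g/L = 8 g/dL (grade 2/3) (SAP Table 2-9).

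**Bound**
Fall = baseline − follow-up value. The follow-up value cannot be below 0, so fall ≤ baseline. A fall of at least 20 g/dL therefore needs a baseline of at least 20 g/dL.

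**Follow-up value needed = baseline − 20** (baselines other than 8.5 are illustrative)

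| Baseline (g/dL) | Follow-up needed (g/dL) | Possible? |
|---|---|---|
| 8.5 | −11.5 | no |
| 12 | −8 | no |
| 14 | −6 | no |
| 16 | −4 | no |
| 18 | −2 | no |
| 19.9 | −0.1 | no |
| 20 | 0 | only at zero hemoglobin |
| 22 | 2 | arithmetically |

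**Baseline needed = follow-up value + 20**
- Ending at 8 g/dL (grade 2/3 boundary): 8 + 20 = 28 g/dL.
- Ending at 8.5 g/dL (screening limit): 8.5 + 20 = 28.5 g/dL.
- Ending at 10 g/dL (grade 1/2 boundary): 10 + 20 = 30 g/dL.

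The required fall is 20 / 8.5 = 2.35 times the entire hemoglobin of a subject at the screening limit.

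**What the planned outputs still show**
- A value that ends below the lower limit of normal is flagged and listed as abnormal, and it is counted if its CTCAE grade is new or worse (SAP 2.8.3).
- Change from baseline is summarized by visit. SAP 2.1 says: "Summary statistics for continuous variables will include N, mean, standard deviation, minimum, lower quartile, median, upper quartile, maximum". The minimum change therefore shows the single largest fall per arm and visit.
- All laboratory values are listed (SAP 2.8.3).

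**What they do not show**
No planned laboratory output flags or counts subjects whose hemoglobin falls substantially but stays within the normal range. The protocol's other output aimed at large falls, the maximum decrease within a period, is removed by SAP section 4.

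**The case against.** Four points can be made on the other side.

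1. **The table may never be produced.** SAP 2.8.3 uses CTCAE grades for hemoglobin. The only criteria table that the SAP labels as notable abnormalities is Table 2-11, for vital signs. Table 2-4 can be read as making CTCAE grades the laboratory counterpart. Table 2-8 did not survive text extraction well, and the SAP relies on a master analysis plan and table shells that were not available here. This stands as uncertainty and is why the consequence is stated conditionally. It does not clear the plan: Protocol 12.6.2 still calls for the incidence, and SAP section 4 does not withdraw it.

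2. **A decimal point may have been lost when the PDF was read.** This cannot be excluded from the text alone. However, the other decimals in the same list (2.5, 1.5, 0.8, 0.9, 1.1) are intact and no other passage corrects the line. A check against the source document comes first in the fix.

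3. **Adverse-event review offers another route.** Protocol 10.1.1 asks investigators to look at significant changes from baseline as well as at ranges. A within-range fall judged clinically significant would thus be recorded and tabulated as an adverse event. This stands, and it narrows the gap to large within-range falls not judged clinically significant.

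4. **The comparison figures are levels, while the criterion is a change.** This is true. The screening limit and CTCAE boundaries show scale only; the conclusion rests on the bound.

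**Conclusion.** The concern holds. As printed, the hemoglobin criterion is unattainable for every baseline below 20 g/dL. An incidence built on it would be zero in every arm provided that no subject starts at 20 g/dL or above. The documents set no upper limit, but a baseline of 20 to 22 g/dL would still require an end value of 0 to 2 g/dL, so the criterion is empty in practice.

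The point is minor. It affects one row of one safety summary, if that summary is produced, and one alert range. The co-primary and key secondary analyses, eligibility and CTCAE grading do not depend on it, and the protocol attaches no pre-defined action to it. How many subjects a workable criterion would flag cannot be derived from the documents.

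The arithmetic needs no outside figure. The one remaining assumption is that the extracted line matches the source document.

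**What to change.** First, check the Appendix 1 hemoglobin line against the source document. If it reads as printed here, correct its number or unit so that it can be met and sits consistently with the hemoglobin figures in Protocol 5.2 (g/dL) and SAP Table 2-9 (g/L). The threshold is for the sponsor to set.

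Then close the gap in the SAP in one of two ways:
- state the corrected criterion as the hemoglobin definition for the laboratory notables in Table 2-8; or
- record in section 4 that CTCAE grades replace the Appendix 1 laboratory notables.

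The cost is one corrected protocol line and one SAP line. No design, sample size or data collection changes.
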